4 METHODOLOGY

- 4.3 Study Details and Procedures
- 683 **Study Design and Sampling**: This is a single arm, open-label Phase I, non-randomized study.
- Participants meeting the inclusion criteria will be sequentially enrolled.

685

681

- 686 **Study Population:** The study population will be up to 16 women 18 years or older living in
- Kisumu County in Kenya, in order to have 12 fully evaluable participants, our desired sample
- size. Fully evaluable participants are those who receive artesunate inserts for 5 consecutive days
- and undergo blood draws before and after receiving artesunate at all the timepoints per study
- 690 protocol. Enrollment will stop once data from 12 fully evaluable participants are obtained. No
- more than 16 participants will be enrolled.

692 693

694

695

696

697

698

699 700

Inclusion Criteria

- 1. Age 18 years or older
- 2. Negative pregnancy test at screening
- 3. Weight ≥50 Kg at study entry*
- 4. Willingness to use contraception (hormonal or barrier) during the 5-day study dosing phase if of childbearing age (less than 50 years of age)
- 5. Ability and willingness to provide informed consent
- 6. Plan to reside in the study location during the study period
- *Justification for weight criteria: A minimum body weight of 50Kg will meet the planned artesunate dosing of ≤ 4 mg/Kg for which excellent safety data is available.

702 703 704

705

706

707

708

709

710

711

712

713

701

Exclusion Criteria

- 1. Current pregnancy or breastfeeding status
- 2. History of total hysterectomy
- 3. Known allergy to Artesunate
- 4. Have a medical comorbidity that in the opinion of the investigator would interfere with study participation
- 5. Currently receiving artemisinin-based agents for malaria treatment or completed artemisinin-based treatment within the previous 3 days.*
- Male at birth
 - 7. Current use of efavirenz antiretroviral therapy
- 714 8. Positive malaria antigen test at screening
- *Based on dihydroartesunate (artesunate's active metabolite) half-life of between 0.5-1.5 hours²⁹
- 717 **Study Location:** The study will be carried out at the Lumumba Sub-County Hospital and at the Victoria Biomedical Research Institute in Kisumu, Kenya.
- Recruitment: Participants will be recruited from among women in the general population within the vicinity of the study location, including within health facilities in Kisumu County in Kenya.
- 721 The study team will include a brief description of the study as part of outreach activities and
- 722 educational talks at surrounding facilities. Participants interested in participating will be screened
- 723 for eligibility individually. The informed consent and all study procedures will be carried out in a
- private area before any study activities are performed.

725 726

Schedule of Events

	SCREENING/ENRO LLMENT VISIT	Visit 1 ¹	VISITS 2-4	VISIT 5	VISIT 6 ²
Informed Consent	X				
Assess Eligibility	X				
Review and record demographic and medical History	X				

Assign unique participant ID number	X				
Pelvic exam	X				
Malaria antigen testing ²	X				
Urine pregnancy testing	X				
Collect locator information	X	X	X	X	
Demonstration of intravaginal Artesunate application using pelvic model	X	X			
Artesunate pessary self-administration in clinic		X	X	X	
Review concomitant/prohibite d medications	X				
Blood Draw(s)		X		X	
Adverse events review		X	X	X	X
Transport Reimbursement	X	X	X	X	X
Study exit					X

727 1. Visit 1 may be combined with the screening visit

2. Those positive will be referred for treatment and be screen failure

*Visit 6 will occur 4-10 days after visit 5

a. 4.2 Study Activities by Visit

730 731 732

733

734

735

736

737

728 729

Pre-Screening: As part of participant outreach and recruitment, study staff can pre-screen potential study participants at either on-site or off-site locations. During these interactions, study staff may explain the study to potential participants and ascertain elements of presumptive eligibility to be confirmed at an on-site screening visit. Process information (e.g., number of potential participants contacted, number presumptively eligible) may be recorded and stored at study sites in the absence of written informed consent from potential participants, provided the information is collected in such a manner that it cannot be linked to participant identifiers.

740 **Screening/Enrollment Visit:** The screening period may be up to 14 days prior to Visit 1.

- Multiple visits may be conducted to complete all required screening procedures, if necessary.
- Written informed consent for screening/enrollment must be obtained before any screening
- procedures are initiated. For participants who do not meet the eligibility criteria, screening will
- be discontinued once ineligibility is determined, and a screen failure recorded. As part of
- screening activities, participants will have a malaria antigen test to screen for subacute malaria
- infection. Those who test positive will be referred for treatment and considered screen failure.

747 748

749

750

751

752

753

754

755

756 757

758

Screening/enrollment visit activities:

- Confirm eligibility
- Obtain informed consent
- Assign unique participant ID number
- Study protocol counselling (introduce the study to the participant, explain all study activities and timing, length, expectations of the participant, demonstration of intravaginal *Artesunate* application using pelvic model, discussion of tampon use etc.)
- Perform limited physical and pelvic exam and colposcopy with digital imaging
- Collect locator information
- Urine pregnancy testing
- Review concomitant/prohibited medications
- Obtain basic demographic and clinical data

759 760 761

762

Visit 1: Visit 1 can occur on the same day or up to 14 days following the screening/enrollment visit. Visit 1 will be timed to be no less than 1 week before the participant's anticipated menstrual cycle, for menstruating participants.

763764765

766

767 768

769 770

771

773

774

Visit 1 activities:

- Confirm eligibility
- Update locator information (if necessary)
- Review artesunate self-administration instructions and study protocol
- Review concomitant/prohibited medications
- Draw blood (~2.5ml) before artesunate self-administration
 - Artesunate self-administration using applicator, followed by tampon
- Observation for 30 minutes
 - Provide transport reimbursement
 - Schedule Visits 2

775 776

Visit 2-4: Visits 2, 3 and 4 must occur sequentially (within 24 hours) of each other. Attempts will be made to start visits at approximately the same time each day.

777 778 779

780

781

784

Visit 2-4 activities:

- Update locator information (if necessary)
- Review and record adverse events using standardized questionnaire
- Perform pelvic exam as needed based on AEs described (pelvic exam for suspected grade II or worse AEs)
 - Review concomitant/prohibited medications

- Artesunate self-administration using applicator, followed by tampon insertion
- Observation for 30 minutes
 - Provide transport reimbursement
 - Schedule subsequent visit

789 790

785

786

787

788

Visit 5: Visit 5 will occur one day (~24 hours) after Visit 4. Attempts will be made to start visits at the same time each day.

791 792 793

794

795

796 797

798

799

800 801

Visit 5 activities:

- Update locator information (if necessary)
- Review and record adverse events using a standardized questionnaire
- Perform pelvic exam as needed based on AEs described (pelvic exam for suspected grade II or worse AEs)
- Review concomitant/prohibited medications
- Draw blood (~2.5ml) before artesunate self-administration & insert peripheral cannula for subsequent blood draws
- Artesunate self-administration using an applicator, followed by tampon insertion
- Blood draws (~2.5ml each time) at 15, 30min, 1h, 2h, 4h, 6h, and 8h after artesunate self-administration.
 - Provide transport reimbursement
- 805 Schedule visit 6

806 Visit 6: Visit 6 will occur 4-10 days after visit 5

807 808

809

804

Visit 6 activities:

- Review and record adverse events since last visit using standardized questionnaire
- Perform pelvic exam and colposcopy with digital imaging
- 811 Study exit/termination
- 812 Provide reimbursement

813814

817 818

819

820

b. 4.3 Adverse Event Reporting

815 **Definitions** 816 An adverse

An adverse event (AE) is any untoward medical occurrence in a patient or clinical investigation participant administered a pharmaceutical product and which does not necessarily have a causal relationship with this treatment. An adverse event can therefore be any unfavorable and unintended sign (including an abnormal laboratory finding), symptom, or disease temporally associated with the use of a medicinal (investigational) product, whether or not related to the medicinal (investigational) product.

821 822 823

824

825

An unexpected (unlisted) adverse event is an adverse reaction, the nature or severity of which is not consistent with the applicable product information (e.g., Investigator's Brochure for an unapproved investigational product or package insert/summary of product characteristics for an approved product).

826 827 828

A serious adverse event (SAE) is any untoward medical occurrence that at any dose:

PI: [name] Version 1.0

- 829 results in death;
- 830 is life-threatening;
- * requires inpatient hospitalization or prolongation of existing hospitalization;
- results in a persistent or significant disability/incapacity; or
 - is a congenital anomaly/birth defect

833 834 835

Important medical events as assessed by medical and scientific judgment may also be considered SAEs by the investigator and should be reported in an expedited fashion.

836 837 838

839

840

841 842

843

844 845

846

847 848

849

850

851

852

853

854 855

856

Safety/Adverse Events Evaluations: Safety evaluation to evaluate for adverse events will be done using U.S National Cancer Institute Common Terminology Criteria for Adverse Events, v5.0 (CTCAE 5.0) (Appendix B) for systemic AEs⁶⁹ and the Division of AIDS Female Genital Grading Table for Use in Microbicide Studies (Appendix C) for localized/genital AEs. 70 Adverse events will be elicited by a trained clinician (nurse, clinical officer, or medical officer) at the study visits 1 through 6. As part of AE evaluation, systemic symptoms that may be related to study drug use including headache, dizziness, tinnitus, GI discomfort will be evaluated. Localized/pelvic AEs including vaginal pruritis, discharge, pelvic pain will also be elicited during study visits. All participants will have a pelvic and speculum exam at baseline to document the appearance of genital mucosa before artesunate administration. During visits 1-5, pelvic/speculum exam will be performed based on clinical indications only, including among all participants reporting suspected grade 2 or higher local AEs including pain, irritation, itching, or erythema, based on the Division of AIDS Female Genital Grading Table for Use in Microbicide Studies standardized grading scale. Clinicians will have a low threshold for performing a pelvic exam during these visits based on participant symptoms. At visit 6 (study exit), all participants will have a pelvic exam to document appearance of genital mucosa at end of artesunate use. During pelvic examinations, the vulva, vaginal tissue and cervix will be inspected for evidence of inflammation or erythema. Per the CTCAE and Division of AIDS standardized grading scales, AEs will be graded as grade 0- none. grade 1 – mild, grade 2 – moderate, grade 3 – severe, grade 4- potentially life-threatening, or grade 5 – death-related AEs.

857 858 859

860

861 862

863 864

865

866

867 868

869

870

Management and reporting of adverse events: Based on the prior Phase I study of intravaginal artesunate at this dosage and frequency, self-limited grade 1 (mild) AEs are expected, and grade II (moderate) AEs will be few, while grade 3 or worse AEs are not expected. In this study, AEs will be elicited and recorded in the participant study records at each study visit. All local AEs will be considered causally related to administration of the study drug. Causality of all other AEs will be assessed individually. Participants with grade I or II AEs will be followed until resolution of AEs. Grade II AEs will be managed symptomatically. Vaginal infections including yeast infections will be treated with oral medications during the dosing phase. Significant local inflammation, if any, will be treated with oral analgesics. Local infection or ulceration, which are unexpected, will be treated with routine wound care and antibiotics as necessary. Participants found to have any grade 3 or higher AEs will be instructed to stop study drug use, and the Data and Safety and Monitoring Board (DSMC) notified within 5 business days of the PI become aware. Participants will not resume study drug use until the DSMC decides that the AE is not related to the study drug.

871 872 873

874

Outcomes of AEs will be assessed as: 1) Recovered, 2) Recovered with sequelae, 3) Ongoing at participant end-of-study visit, 4) Died, 5) Unknown.

Pregnancies detected during the study (after first use of Artesunate (Visit 1) through Visit 5) will be recorded as SAEs. The participant will be referred for prenatal care, preferably to a provider who is experienced in reproductive toxicity for further evaluation and counseling. The Investigator will attempt to follow the participant until completion of the pregnancy and document the outcome of the pregnancy (either normal or abnormal outcome) and report the condition of the fetus or newborn to the Study Coordinator, if possible. If the outcome of the pregnancy was abnormal (e.g., spontaneous or therapeutic abortion), the Investigator will report the abnormal outcome as an AE.

For all adverse events reported or observed, the information should be recorded in the Case Report Forms for that participant. This will include a full description of the event, its seriousness, its severity or toxicity grade (intensity), the relationship to the study drug, and the treatment, outcome, and sequelae of the event.

Any serious or unexpected event, which occurs to any participant in the course of her treatment on this study or within 30 days following cessation of treatment, must be reported immediately to the Study Coordinator by telephone at [name] or within 24 hours of the investigator learning of its occurrence. The immediate reports should be followed promptly by detailed, written reports. The Study Coordinator will then inform the Principal Investigator of the Adverse Event The PI is responsible for reporting AEs.Copies of these reports should be sent to:

• IRB

Reporting is required of all unanticipated problems to the UNC IRB, including those which may occur after the participant has completed or has withdrawn from the study, including after study closure.

Funding Source (if appropriate)

Unanticipated problems as defined by the UNC IRB:

903 Un 904 (U

Unanticipated problems involving risks to participants or others" or "Unanticipated Problem" (UP) refers to any incident, experience, or outcome that:

 is unexpected (in terms of nature, severity, or frequency) given (a) the research procedures that are described in the protocol-related documents, such as the IRB-approved research protocol and informed consent document; and (b) the characteristics of the participant population being studied;
 is related or possibly related to a participant's participation in the research; and

 suggests that the research places participants or others at a greater risk of harm (including physical, psychological, economic, or social harm) related to the research than was previously known or recognized.

Unanticipated Problems that are serious adverse events should be reported to the UNC IRB within one (1) week of the investigator becoming aware of the event. Any other Unanticipated Problem should be reported to the UNC IRB within two (2) weeks of the investigator becoming aware of the problem. If the Unanticipated Problem Report cannot be completed in its entirety within the required time period, a preliminary report should be submitted. The Unanticipated Problem Report should be amended once the event is resolved and/or more information becomes available.

PI: [name] Version 1.0

All individual AE and IND Safety Reports shall be maintained by the Principal Investigator. For those events that are not reportable to the UNC IRB, a summary (i.e., not individual reports) of all adverse events that have occurred within the last approval period should be submitted to the UNC and Kenya IRB's at the time of continuing review.

Reports from a Data and Safety Monitoring Committee, (DSMC), or other independent safety monitoring group should be provided to the UNC and Kenya IRBs on a regular basis, generally at least as often as the study undergoes continuing review. Reports should include findings from adverse event reports and recommendations derived from data and safety monitoring.

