1.4 Effect of malaria infection status on artesunate and DHA pharmacokinetics

353 A direct comparison among healthy and parasitaemic subjects was conducted by Teja-Isavadharm et al, who studied the PK of DHA following oral AS administration in six healthy 354 adults and six adult falciparum malaria patients. 43 The investigators determined that AUC and 355 356 Cmax of DHA were significantly higher in subjects with malaria as compared to healthy 357 subjects. Binh et al obtained similar results when comparing the PK in eight patients with falciparum malaria and ten healthy subjects. 44 However, given the relatively small size of both 358 studies, definitive conclusions regarding differences in PK between healthy and infected subjects 359 cannot be drawn at this time.³³ However, as DHA clearance is dependent on hepatic blood flow, 360 361 a reduction in clearance, and consequently an increase in exposure associated with acute malaria 362 infection would be consistent with known DHA's PK properties.³³

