Excessive participant withdrawals from protocol therapy or from the study can render the study un-interpretable; therefore, unnecessary withdrawal of participants should be avoided.

Participant Lost to Follow up: A participant will be considered lost to follow-up if he or she fails to return for three scheduled study visits and is unable to be contacted by the study site staff.

The following actions must be taken if a participant fails to return to the clinic for a required study visit:

- The site will attempt to contact the participant and reschedule the missed visit and counsel
 the participant on the importance of maintaining the assigned visit schedule and ascertain if
 the participant wishes to and/or should continue in the study.
- Before a participant is deemed lost to follow-up, the investigator or designee will make every
 effort to regain contact with the participant (where possible, 3 telephone calls and, if
 necessary, a home visit by the study team if permission is obtained for home visit at study
 entry, or local equivalent methods). These contact attempts should be documented in the
 participant's medical record or study file.
- Should the participant continue to be unreachable, he or she will be considered to have withdrawn from the study with a primary reason of lost to follow-up.

Off-Study Criteria: Participants will be considered off study and will no longer be followed on the protocol for any reason if any of the following criteria are met: when the participant reaches the end of the study as defined by the Schedule of Events Table, participant withdraws consent for treatment and any further data collection, death, or lost to follow-up.

1074
1075 **Malaria treatment during dosing phase (Day 1-5):** If study participants are diagnosed with
1076 malaria during the Artesunate pessary dosing phase (day 1-5), a non-ACT treatment will be used
1077 to avoid PK studies confounding. Participants will be encouraged to sleep under a mosquito net
1078 to reduce the chance of new malaria infection during the study.

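### The only malaria antigen test can be up to 18 days old at the Day 5 PK profile, so a symptomless new infection can enter the primary DHA AUC; the size of the effect is uncertain

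*Combined protocol and SAP*

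**What the plan says.** Exclusion criterion 8 in Section 4 reads "Positive malaria antigen test at screening". Section 4.2 gives the purpose: as part of "screening activities, participants will have a malaria antigen test to screen for subacute malaria" infection, with positive women referred and counted as screen failures. In the Schedule of Events the row "Malaria antigen testing" is marked in the screening/enrolment column only, and the Study Schema (Section 2.4) likewise lists the test only there.

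On timing, Section 4.2 states that "The screening period may be up to 14 days prior to Visit 1". In the same section, "Visit 1 can occur on the same day or up to 14 days following the screening/enrollment visit", and the dosing visits then run on consecutive days: "Visit 5 will occur one day (~24 hours) after Visit 4". The serial blood draws are at Visit 5.

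Section 1.4 reports from a small direct comparison that AUC and "Cmax of DHA were significantly higher in subjects with malaria as compared to healthy" subjects. It adds that the studies are too small for definitive conclusions. For infection that shows itself during dosing, Section 4.4 says that if a participant is diagnosed with "malaria during the Artesunate pessary dosing phase (day 1-5), a non-ACT treatment will be used", so as not to confound the PK data, and it encourages use of mosquito nets.

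**The concern.** The antigen test is there to keep infections that cause no obvious illness out of the PK sample, but nothing ties its date to the dosing or to the profile. Visit 1 asks staff to confirm eligibility again. Because criterion 8 refers to the screening result, a negative result two weeks old still satisfies it. A wait is plausible: Visit 1 must fall at least a week before expected menses, so some women screened at other times in their cycle will have to wait.

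No later step closes the gap. The provisions for malaria on Days 1-5 depend on a diagnosis. The definition of a fully evaluable participant requires five daily inserts and all blood draws, and sets no malaria condition. An infected woman's profile would therefore enter a primary endpoint that Section 2.2 defines in healthy women and Section 4.5.2 tests against historical values. Section 1.3 reports those values separately for healthy adults and adults with malaria. Any bias would most likely be upward, overstating exposure, and with 12 women a single high profile would also widen the SD.

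**Working it through.** **1. Age of the test.** Screening to Visit 1 is 0 to 14 days (Section 4.2). Visit 1 to Visit 5 is 5 - 1 = 4 days. Test to first insert is therefore 0 to 14 days, and test to PK profile 0 + 4 = 4 to 14 + 4 = 18 days. The protocol prints the 14 days; the 18 follows from it.

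**2. Shift in the mean from one infected woman of 12.** With r the ratio of DHA AUC in malaria to that in healthy adults, the relative shift is (r - 1)/12. Section 1.3 gives these figures in ng*hr/ml:

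| Route and dose | Healthy | Malaria | r | Shift |
|---|---|---|---|---|
| Oral, 200 mg | 1158-1331 | 3027 | 3027/1331 = 2.27 to 3027/1158 = 2.61 | 10.6% to 13.4% |
| IV, 120 mg | 1850 | 1845-2377 | 1845/1850 = 1.00 to 2377/1850 = 1.28 | 0% to 2.4% |

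Both ratios compare different studies. No vaginal figures exist.

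**3. Effect on the SD.** The documents give no between-woman variation, so a CV of 30-50% is assumed. With the healthy mean set to 1, the expected sample variance with one infected woman is [11·CV² + (r·CV)²]/12 + (r - 1)²/12. At the oral ratios the SD rises 1.69- to 1.97-fold for a CV of 30% and 1.37- to 1.53-fold for a CV of 50%. At the top IV ratio (1.28) it rises 1.06- and 1.04-fold.

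**4. Chance of at least one new infection among 12 women.** The documents give no incidence, so 0.25, 0.5 and 1 infection per person-year are assumed. The formula is 1 - exp(-rate × 12 × days/365).

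| Days from test to profile | 0.25 | 0.5 | 1 |
|---|---|---|---|
| 18 (all 12 women wait the full 14 days) | 14% | 26% | 45% |
| 4 (test on the day of Visit 1) | 3% | 6% | 12% |

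The first row is an upper bound at each rate, because women screened and dosed on the same day already have a 4-day gap. Both rows count every new infection, including symptomatic ones that might be diagnosed.

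**5. Chance and shift together.** At 0.5 per person-year and 18 days, the expected number infected is 12 × 0.5 × 18/365 = 0.30. Multiplied by the shifts in step 2, the expected shift in the mean is 3-4% on the oral figures and 0-0.7% on the IV figures.

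**The case against.** The strongest objection concerns size. The oral ratio is the larger of the two that the protocol offers, and on the IV figures one infected woman barely moves the mean. Both sets come from adults described as having malaria. Section 1.4 links the likely mechanism, reduced DHA clearance, to acute infection. A woman that ill would attend clinic on five consecutive days, with an interval history each time and adverse event review, and might well be diagnosed. The women who go unnoticed are those for whom the documents give no PK effect. All of this stands.

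It can also be said that the Visit 1 list already requires eligibility to be confirmed, and that a missing bullet is weak evidence because the screening bullets omit the malaria test too. The second half is fair. However, the schema and the Schedule of Events both show a single test, and confirming a criterion worded for screening does not call for a new one.

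A reader might infer that the primary AUC will be inflated by 11-13%, or that contamination is close to an even chance. The documents support neither. The first takes only the oral figures and applies an effect seen in malaria patients to symptomless women. The second needs the highest assumed incidence and all 12 women at the maximum gap.

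Finally, moving the test has a price: a positive woman is now referred at screening, and under the change she would be found later. This also stands and is counted below.

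**Conclusion.** The gap is real and can be read directly from the schedule. A symptomless infection acquired after screening can enter the primary DHA AUC, with a test that is up to 14 days old at the first insert and 18 days old at the profile. The consequence is uncertain, from nil to moderate: 0-2.4% or 11-13% on the mean per infected woman of 12, depending on which of the protocol's figures is used, and possibly less for symptomless infection. The probabilities rest on assumed incidence, a constant rate, and, for the upper values, every woman waiting the full 14 days. The point justifies an inexpensive change of timing. It does not show that the primary analysis is invalid.

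**What to change.** When screening and Visit 1 are separate, do the single planned antigen test at Visit 1, with the result read before the first insert. Reword exclusion criterion 8 to: *Positive malaria antigen test at Visit 1 before first insert*. Make matching edits in the Study Schema (Section 2.4), the Schedule of Events and its footnote on positive results, and the screening text and Visit 1 activities in Section 4.2. A same-day result should be workable, because the protocol already allows screening and Visit 1 to be combined. Do not assume that the Visit 1 PK sample can serve for the antigen test: Section 4.4 has that blood centrifuged and stored for the assay, and nothing says that it suits both uses.

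The number of tests stays the same and the longest gap from test to profile falls from 18 to 4 days. The costs are:

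- Some screening effort is spent on women who then test positive.
- A positive woman is identified and referred up to 14 days later than now, which the investigators need to weigh.
- The amendment touches several places and, under Section 5.1, needs approval from all the regulatory bodies.
- A 4-day untested window before the profile remains, and the change does not settle whether a woman diagnosed on Days 1-5 stays in the primary AUC.
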